Unicompartmental knee arthroplasty (UKA) is a procedure to replace only one tibiofemoral compartment of the diseased knee, most commonly the medial compartment. Overcorrection or undercorrection of limb alignment is due to malpositioning of the components or improper selection of polyethylene thickness. Malalignment of the leg is associated with increased polyethylene wear [Hernigou 2004-A], disease progression to the opposite compartment [Hernigou 2004-A; Jeer 2004; Sarangi 1994; Ridgeway 2002], and implant loosening [Koshino 1991]. In addition to limb alignment issues, malalignment and malpositioning of prosthesis components can lead to early failure [Kasodekar 2006; Barrett 1987; Emerson 1991; Herzog 1991]. Malalignment of the femoral component is known to cause femoral fracture [Sandborn 1987] and tibial component loosening [Assor 2006]. Excessive posterior slope (>7 degrees) of the tibial component is associated with tibial component loosening [Hernigou 2004-B], rupture of the ACL [Hernigou 2004-B], and increased bone stresses [Sawatari 2005]. When performed accurately, UKA performed using minimally invasive surgical (MIS) techniques has been correlated with faster rehabilitation, shorter hospital stays [Carlsson 2006], and better functional results [Muller 2004]. However, MIS UKA is a more technically demanding procedure and smaller incisions reduce visibility, increasing the risk of malalignment. Compared to conventional open UKA, MIS UKA resulted in less accurate implant positioning and limb alignment [Fisher 2003], and resulted in increased rates of revision and non-revision operations [Hamilton 2006]. Robotically guided surgery has been introduced to improve accuracy in less invasive procedures. Robotically guided surgery involves a patient specific 3D plan and accurate tactile burring of the planned implant position. When augmented with robotically guided surgery, UKA produced more accurate and reproducible alignment than with conventional UKA [Coon]. With increased pressures from patients to shorten rehabilitation time, hospital stays, and incision length, successful MIS UKA is a desirable procedure. However, MIS UKA can lead to malalignment of components and early failure. Robotically guided UKA has been shown to improve post-operative alignment. Survivorship of this novel procedure has not yet been reported. This study aims to determine a survivorship of this procedure coupled with a novel, anatomically designed UKA implant at two years post-operative.

SPECIFIC AIM

The specific aim of this study is to determine the survivorship rate of robotically guided MCK medial onlay UKA implants at a two, five, and ten year follow up. Study participants will also be asked about their level of satisfaction with their knee function following their robotically guided UKA procedure.

INCLUSION CRITERIA

All patients over 21 years of age who underwent primary robotically guided UKA and received a medial MCK onlay implant and are at least 24 months post-operative are eligible to participate in the study.

EXCLUSION CRITERIA

Patients will be excluded from participation in the study if they are cognitively unable to answer questions related to their index procedure. There are no other exclusion criteria.

STUDY ENROLLMENT PROCEDURE

Patients will be retrospectively identified and selected to participate in the study based on the following criteria: They underwent a MAKOplasty procedure by the investigating surgeon and received a medial MCK onlay implant. They must be at least 24 months post-operative at the time of the study. The sponsor will provide the study staff with relevant dates of surgery for the study.

Investigator's study staff will review past surgery schedules to identify potential subjects; charts will be pulled to confirm the type of surgery performed. Once this has been done, the study staff will mail eligible subjects a Research Subject Information Sheet to introduce the study. The subject will then be contacted by phone to review the study. The research staff will answer any questions the subject may have and then verbally consent the subject over the phone.. Once the subject has verbally consented, the research staff will continue to ask the subject the 5 research questions. The research staff will document the subject's verbal consent and collect the subject's answers over the phone.

STUDY DESIGN

The purpose of this study is to determine the survivorship and outcomes of medial MCK onlay implant initially at two years post-operative, then at five and ten years post-operative. Once eligible patients are identified, contacted, and consented, they will be asked a series of questions to determine: a) if they have had their original MAKOplasty medial MCK onlay implant revised or reoperated, and b) if they still have their original implant, how satisfied they are with their outcomes. The questions that will be asked of the patients are as follows, in this order:

- Did you have a MAKOplasty medial MCK onlay implant done by [name] on [DOS] on your [side] knee?
 - If yes, have you since had that implant/knee removed, revised, or reoperated for any reason? Response options: Yes, No, Do Not Know
 - If yes, please list the reason and the date of revision.
 - If yes, did you return to the same surgeon that performed your original MAKOplasty procedure to perform your revision procedure?
- How satisfied are you with your knee function on the MAKOplasty operative knee? Response options: Very Satisfied, Satisfied, Neutral, Dissatisfied, Very Dissatisfied.

The investigator is responsible for enrolling approximately 150 subjects. All patient responses will be reported. Patients who respond "do not know" on whether they have had a revision to their original MAKOplasty knee or patients who are lost to follow up will be included in the study for reporting reasons, however we will continue to contact patients until we have a total of at least 100 confirmed responses (yes/no) for the investigating surgeons. Three attempts will be made to contact each patient.

After the third unsuccessful attempt to contact the patient, the patient will be regarded as "Lost to Follow Up".

Basic demographic information such as gender, date of birth, and BMI at time of surgery will also be collected retrospectively from each patient.

PATIENT FOLLOW-UP

All patients who consent to participate in the study will be asked a series of questions related to their original MAKOplasty implant at two years post-operative. Patients will be contacted again with the same series of questions at five years post-operative and ten years post-operative.

RISKS/BENEFITS

This is a minimal risk study which involves collection of data. The purpose of this study is for research purposes only. There is no direct benefit to the patient to participate in this study. The results of this research study may contribute to clinical research overall and may be published.

DATA MANAGEMENT

All data will be collected and entered by approved study staff into a secured, password protected excel spreadsheet. Patients will be assigned a study ID number before being entered into the spreadsheet. A master spreadsheet correlating the patients to their study ID number will be locked and password protected, accessible only by the PI and study staff.

References

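### The single satisfaction item is at risk of upward bias of unknown size: the investigator's own staff ask it aloud, and the PI can link each answer to a patient

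*Protocol*

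**What the plan says.** Study Enrollment Procedure defines who is eligible: "They underwent a MAKOplasty procedure by the investigating surgeon and received a medial MCK onlay implant". It also says who does the work: "Investigator's study staff will review past surgery schedules to identify potential subjects". Study staff mail an information sheet and phone the patient. Research staff answer the patient's questions, take verbal consent, and then "the research staff will continue to ask the subject the 5 research questions"; they are to "collect the subject's answers over the phone".

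In the question list under Study Design, the opening question identifies who performed the operation, its date and the side. The revision question follows. A patient who answers yes is asked for the reason and date, and then: "did you return to the same surgeon that performed your original MAKOplasty procedure to perform your revision procedure". The last item asks how satisfied the patient is with the function of the operated knee, on five options from very satisfied to very dissatisfied. Patient Follow-up repeats the same questions at five and ten years.

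Under Data Management, answers are entered against a study ID. The master file that ties IDs to patients is "accessible only by the PI and study staff".

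**The concern.** Satisfaction is a judgement, and a patient may soften it when speaking to the team of the person who operated, particularly if that person can look up the answer. The protocol describes no self-completed form, no caller independent of the investigator, and no barrier between the PI and individual answers.

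The likely direction of error is upward, in favour of the device and the surgeon. There is one group only, so no contrast exists in which a common shift would cancel. A larger sample would narrow the interval around the shifted value and leave the shift in place. Because the procedure is repeated, the same risk attaches to all three time points. This is how the data are collected, so no later analysis can undo it.

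**Working it through.** The protocol states no expected satisfaction rate, no precision and no interval, so there is no figure to reproduce. The check is of the text first, then of scale under stated assumptions.

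1. *Caller.* Study Enrollment Procedure attributes the screening to the investigator's study staff and the calls to study or research staff. It names no outside interviewer.

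2. *Surgeon and PI.* The protocol does not state that the PI operated. Patients are those of the investigating surgeon, and the staff are the investigator's, so this is the natural reading. It remains an inference, and Study Design also uses the plural for investigating surgeons.

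3. *Linkage.* Answers are coded, not anonymous. The PI may open the key, and no rule keeps the PI from the answers themselves.

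4. *Scale, assumed.* Let *t* be the true share satisfied or very satisfied, and *k* the share of the remaining patients who answer as satisfied. The reported share is *t* + (1 − *t*)*k*, so the shift is (1 − *t*)*k*. Both *t* and *k* are assumptions.

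| *t* | *k* = 10% | *k* = 25% | *k* = 50% |
|---|---|---|---|
| 80% | 82% | 85% | 90% |
| 85% | 86.5% | 88.75% | 92.5% |
| 90% | 91% | 92.5% | 95% |

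The shift runs from 0.10 × 10% = 1 point to 0.20 × 50% = 10 points.

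5. *Against sampling error.* Take *n* = 100, the protocol's minimum number of definite yes/no answers on revision, as the approximate number of satisfaction answers. The exact (Clopper-Pearson) 95% limits for *x* of *n* are the 0.025 quantile of Beta(*x*, *n* − *x* + 1) and the 0.975 quantile of Beta(*x* + 1, *n* − *x*).
   - 85 of 100: 76.5% to 91.4%, half-width (91.4 − 76.5)/2 ≈ 7.4 points.
   - 90 of 100: 82.4% to 95.1%.

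   With a true 80%, a 5-point shift gives an interval that still contains 80%. A 10-point shift gives one that does not.

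6. *What the upper end requires.* At *t* = 80%, 20 of 100 patients are not satisfied. A 10-point shift needs 10 of those 20 to cross. If patients move up by one category only, dissatisfied becomes neutral, and only neutral answers can cross to satisfied. At least 10 of the 20 would then have to be neutral and move. The upper end is therefore demanding.

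7. *Revision, for contrast.* One concealed revision in 100 definite answers raises crude survivorship by 1 point. With 4 true revisions, 96% (90.1% to 98.9%) would become 97% (91.5% to 99.4%).

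**The case against.** The strongest reply is that the documents show a possibility, not a bias. The item asks about knee function, not about the surgeon. Nothing says that the callers took part in the patients' care. The mailed information sheet, which is not among the material reviewed, may already promise that the surgeon will not see individual answers. The range above is assumed throughout, and satisfaction comes second to survivorship in the aim.

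Most of this stands as a limit on the claim. The size is unknown, the identity of PI and surgeon is inferred, and the absence of an assurance to the patient cannot be asserted. What remains is that a promise that the surgeon will not see the answers would not fit Data Management as written, because the PI can open the key. That rule needs changing whatever the sheet says.

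A reader might go further and infer that revision answers are also pushed toward not revised, and that asking about the same surgeon discourages disclosure. The text does not support this. Revision is an event asked for with reason and date, and the same-surgeon question is reached only after the patient has said yes, so it cannot deter that answer. Whether self-reported revisions are checked against records is a separate matter.

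**Conclusion.** The concern holds for the satisfaction item, as a risk of upward bias whose size the documents do not fix. Under the assumptions shown (true satisfaction 80% to 90%, 10% to 50% of the not satisfied answering as satisfied) it lies between 1 and 10 points. The low end is minor. The high end exceeds the half-width of about 7 points computed here for 85 of 100, and no interval reported from these data would reveal it.

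The conclusion rests on the PI being the operating surgeon. If the PI did not operate on a given patient, the linkage part weakens for that patient, and what remains is the spoken interview by the investigator's staff. It would be wrong to say that answers are in fact distorted, or to carry the point over to survivorship with the same force.

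**What to change.** Change Data Management so that identifiable satisfaction answers are held by study staff only. The PI receives them combined or de-identified, with no later look-up. A de-identified extract should not carry the study ID if the PI keeps access to the key. Revision and reoperation reports stay available to the PI.

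Add one line to the call before the satisfaction question, unless the information sheet already says it: *Your surgeon will not be shown your own answer to this question; answers are reported without names.* The line is true only once the access rule has changed, so the two changes go together. It is also compatible with the protocol's intention to report every response.

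Where existing study staff allow, have each call made by someone not involved in that patient's care.

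The cost is one access rule, one sentence and a choice of caller. The PI loses the ability to look up individual satisfaction answers, and the reported satisfaction may be less favourable. The pressure is reduced, not removed, because the callers remain the investigator's staff. If some calls have already been made, record the date of the change, since a fall in satisfaction between time points could otherwise reflect the new procedure.

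### The single failure question pools removal, revision and any reoperation without asking what was done, so implant survivorship cannot be reliably separated from reoperation-free survival

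*Protocol*

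**What the plan says.** The Specific Aim is to "determine the survivorship rate of robotically guided MCK medial onlay UKA implants at a two, five, and ten year follow up". Study Design states two purposes for the telephone questions. Part a) is to learn "if they have had their original MAKOplasty medial MCK onlay implant revised or reoperated". Part b) is to learn, "if they still have their original implant, how satisfied they are with their outcomes".

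The question list under Study Design then contains one failure item: "have you since had that implant/knee removed, revised, or reoperated for any reason". The responses are Yes, No and Do Not Know. A Yes leads to two further items: "please list the reason and the date of revision" and "did you return to the same surgeon that performed your original MAKOplasty procedure to perform your revision procedure". The satisfaction question follows as a separate item.

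Under Patient Follow-Up, "Patients will be contacted again with the same series of questions at five years post-operative and ten years post-operative".

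The background section reports that a cited study of minimally invasive unicompartmental knee arthroplasty "resulted in increased rates of revision and non-revision operations", so the protocol itself treats these as different outcomes.

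**The concern.** Implant survivorship and freedom from any reoperation are different quantities. The first fails when a component is removed or exchanged. The second also fails when the knee is operated on and the implant stays in. The failure item merges the two, and both follow-up items are worded as though every Yes were a revision. A patient reoperated without revision is asked for the date of a revision that never took place.

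Two results are at stake. One is the survivorship rate, if it means retention of the implant as the aim suggests. The other is the satisfaction result in part b), which is tied to patients who still have the original implant; a Yes does not show whether a patient is one of them. Because the same script is used at two, five and ten years, the gap runs through all three time points.

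**Working it through.** The protocol states no expected revision rate, precision target or power, so there is no figure of its own to reproduce. The check has two parts.

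**What the script captures.** The enrolment section announces five research questions and the list contains five:

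| Item | Shows which operation was done? |
|---|---|
| Confirms the index procedure, date and side | No |
| Removed, revised or reoperated (Yes / No / Do Not Know) | No: three outcomes, one answer |
| Reason and date | Only if the free-text reason happens to reveal it |
| Same surgeon or not | No |
| Satisfaction | No |

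The only chart step described takes place before contact and confirms the type of index surgery. No retrieval of later operative records is described. The terms also shift: part a) covers revision or reoperation, while the follow-up items, and the later paragraph on patients who answer Do Not Know, call the same answer a revision.

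**How much this can matter.** Inputs from the protocol: at least 100 confirmed yes/no answers, and about 150 enrolled (an upper case that supposes all of them give a yes/no answer). Assumptions, since the documents give no rates: *k* = 5 patients answer Yes with an event by the time point; *m* of them give a reason that does not reveal the procedure; the other *k* − *m* are component removals; recall is correct. Crude proportions among confirmed responders:

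- lower limit, every Yes a failure: (n − k)/n
- upper limit, every unclear Yes an implant-retaining operation: (n − k + m)/n
- width: m/n

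| m | n = 100 | n = 150 |
|---|---|---|
| 1 | 95/100 to 96/100 = 95–96% | 145/150 to 146/150 = 96.7–97.3% |
| 3 | 95/100 to 98/100 = 95–98% | 145/150 to 148/150 = 96.7–98.7% |
| 5 (worst case) | 95/100 to 100/100 = 95–100% | 145/150 to 150/150 = 96.7–100% |

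Each implant-retaining reoperation counted as a failure lowers the estimate by 1/100 = 1.0 point, or 1/150 = 0.67 points.

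For scale, sampling error:

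- n = 100: standard error √(0.95 × 0.05/100) = 2.18 points; exact 95% interval for 95/100 is 88.7–98.4%.
- n = 150: standard error √(0.9667 × 0.0333/150) = 1.47 points; exact 95% interval for 145/150 is 92.4–98.9%.

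At m = 3 the widths (3.0 and 2.0 points) exceed one standard error, but both ranges lie inside the exact 95% intervals. At m = 5 the upper limit of 100% lies outside them.

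For part b), k = 5 and m = 3 leave between 95 and 98 of 100 responders who still have the original implant. None of these ranges covers patients who answer Do Not Know or are lost to follow-up.

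**The case against.** The best reply is that the item does what part a) asks. If the intended event is revision or reoperation, the composite is measured directly and only the naming is loose. That is right as far as the composite goes, and choosing the event definition can be left to an analysis plan. It does not help part b), whose group depends on the implant still being in place, nor the aim if it means implant retention. An analysis plan cannot supply a field the call never collected.

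Second, the free-text reason will sometimes settle the matter; loosening, for example, suggests a component revision. Reasons such as pain or infection may not. The claim is only that the separation is unreliable, not that it is never possible.

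Third, the effect is modest, and this stands. The counts are assumed; at m = 3 the range sits within the 95% interval; the error from counting every Yes as a failure runs against the implant; and the protocol sets no comparator or threshold. The effect on part b) is likewise confined to the few unclear Yes answers, and no shift in the satisfaction result has been shown. The background sentence describes another study and does not define this one's endpoint; it shows only that the distinction was known.

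Fourth, a new question still relies on patient recall. That also stands. The same-surgeon item may allow some cases to be checked in existing records, but the protocol does not describe doing so.

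**Conclusion.** The concern holds and should be fixed; it does not invalidate the study. As scripted, the calls give freedom from removal, revision or any reoperation. They do not reliably give implant survivorship, nor the group that part b) defines. The uncertainty equals the share of confirmed responders with an unclassifiable Yes: 3 points with 3 such patients in 100, up to 5 points if all of 5 are unclear. These counts are illustrative, rest on correct recall and leave out non-responders. If no patient has an implant-retaining reoperation, the two quantities coincide. If every Yes is counted as a failure, implant survivorship can only be understated among these responders.

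**What to change.** Replace the pooled item with two questions: first, whether any part of the implant has been removed, exchanged or converted to another knee replacement, with the date; second, whether there has been any other operation on that knee, with its type and date. Base implant survivorship and the satisfaction group of part b) on the first. Report freedom from any reoperation, using both, as a separately labelled result. Use the same terms in the Specific Aim, Study Design and the follow-up items.

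The minimum version is one added question after a Yes: which operation was done, and was any component removed or exchanged? Checking the chart where the patient returned to the same surgeon is a useful option.

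The cost is a slightly longer call, a few more data fields and an amendment to the script. The minimum version burdens only patients who answer Yes. Operations done elsewhere would still rest on recall.

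### The failure item asks for one date of revision after pooling all operations since surgery, so the first qualifying date of a knee operated on more than once may not be collected (minor)

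*Protocol*

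**What the plan says.** The Specific Aim is to "determine the survivorship rate of robotically guided MCK medial onlay UKA implants at a two, five, and ten year follow up". The data come from a short telephone script whose wording and sequence the Study Design section fixes: "The questions that will be asked of the patients are as follows, in this order".

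The failure question in that script is: "If yes, have you since had that implant/knee removed, revised, or reoperated for any reason? Response options: Yes, No, Do Not Know". It pools three kinds of event and looks back to the index surgery. The follow-up to a yes is "If yes, please list the reason and the date of revision". This is singular and names only one of the three kinds. A further item asks whether the patient went back to the same surgeon for the revision.

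Two passages bear on when the first call takes place. Study Enrollment Procedure says of the patients: "They must be at least 24 months post-operative at the time of the study". It gives no upper limit. Patient Follow-Up says that consenting patients "will be asked a series of questions related to their original MAKOplasty implant at two years post-operative". It then adds: "Patients will be contacted again with the same series of questions at five years post-operative and ten years post-operative". Data Management has answers entered under a study ID.

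**The concern.** A survivorship estimate needs the date of the first event that counts as failure. The gate question covers any operation on the knee, but the date item asks for one date and calls it the date of revision. A patient who had a reoperation and later a revision can answer that item fully and correctly by giving the later date.

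If the earlier operation counted as failure and lay before a reporting time point, the knee would be recorded as surviving that time point. The error mainly runs one way, towards higher survivorship. A statistical analysis plan can say which of two recorded dates to use, but it cannot supply a first date that the caller did not collect. The protocol offers little by way of backup. Charts are pulled to confirm the type of index surgery, the other retrospective items are demographic, and the script itself expects that some revisions were done by another surgeon.

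**Working it through.** The protocol states no expected survivorship, precision or failure rate, so there is no figure of its own to reproduce. The check has three parts.

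**1. When a knee is misdated.** All of these must hold:
- the knee has at least two operations that meet the failure definition;
- one falls before the time point and one after it;
- both precede the call that first records the failure;
- the patient names the later one.

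Take a reoperation at month 20 and a revision at month 30, and suppose that any reoperation counts as failure.

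| First call | Operations that exist at the call | Date the item can yield | Two-year status |
|---|---|---|---|
| Month 24 | Month 20 only | Month 20 | Failed (correct) |
| Month 36 | Months 20 and 30 | Month 30, if the revision is named | Surviving (wrong) |

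The month-36 call is allowed, because eligibility has a lower limit of 24 months and no upper one. The same pattern can arise at five years if that contact is missed and the patient is reached at ten years.

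**2. Effect of one misdated knee.** The inputs are the minimum of 100 confirmed responses and the enrolment of about 150, both from Study Design, and an assumed 4 true failures by two years. Survivorship = 1 − failures/n, with exact (Clopper-Pearson) 95% limits.

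| n | Misdated | Survivorship | 95% limits |
|---|---|---|---|
| 100 | 0 | 1 − 4/100 = 96.0% | 90.1 to 98.9 |
| 100 | 1 | 1 − 3/100 = 97.0% | 91.5 to 99.4 |
| 100 | 2 | 1 − 2/100 = 98.0% | 93.0 to 99.8 |
| 150 | 0 | 1 − 4/150 = 97.3% | 93.3 to 99.3 |
| 150 | 1 | 1 − 3/150 = 98.0% | 94.3 to 99.6 |

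The shift per knee is 1/100 = 1.0 point or 1/150 = 0.67 point, whatever number of failures is assumed.

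**3. Expected size.** None of these rates is in the protocol; all are assumptions:
- p, failure by two years: 2% to 10%;
- q, share of those failed knees with a second operation before the call that first records the failure: 5% to 20%;
- r, share of those patients who name the later operation: 50% to 100%.

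Expected bias in points = 100 × p × q × r. Chance of at least one misdated knee among 100 = 1 − (1 − pqr)^100.

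| p | q | r | Bias (points) | Chance of at least one |
|---|---|---|---|---|
| 0.02 | 0.05 | 0.5 | 0.05 | 5% |
| 0.05 | 0.10 | 0.5 | 0.25 | 22% |
| 0.05 | 0.10 | 1.0 | 0.50 | 39% |
| 0.10 | 0.20 | 1.0 | 2.0 | 87% |

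The formula treats every such second operation as falling after two years, so it is, if anything, too large. If every first call were made at 24 months, q would be zero for this error and so would the two-year bias.

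**The case against.** The strongest reply is that on the schedule in Patient Follow-Up the problem hardly arises. A call at two years finds only operations done by then, so any date given puts the failure before the time point. This stands as a limit on how often the error occurs. It does not remove it, because the enrolment text permits a later first call and patients are found retrospectively from past surgery schedules.

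Second, a reader might infer that the script allows only one entry. It does not say so. A caller could note several operations, and nothing restricts the spreadsheet. The supportable statement is that nothing asks for the first operation or for all of them.

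Third, the aim concerns survivorship of implants. If failure means removal or revision of the implant, a reoperation that left it in place is not a failure, and the date of revision is the right date in the month-20/month-30 example. This also stands: in that sequence the harm depends on whether reoperation counts. Two successive revisions on either side of a time point would remain ambiguous under either definition.

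Fourth, because the same since-surgery question is repeated at five and ten years, a reader might infer that a failure already reported could later turn into a survivor. The protocol does not support that. The earlier answer is on file under the study ID, and nothing says that a later answer replaces it. What remains is that two calls may give different dates. A rule for resolving them could properly sit in an analysis plan that is not at hand. Repeating the full look-back also has a merit: it catches operations in patients who were missed or who under-reported before.

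**Conclusion.** The point holds as a minor one. The date item is narrower than the question that leads to it, so the first qualifying date may go uncollected for a knee with several operations. The harm is confined to knees with qualifying operations on both sides of a time point before the call that first records the failure. This requires a late first call or a missed contact.

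Each such knee adds 1.0 point to survivorship at 100 responses and 0.67 at 150. On the assumed rates the expected two-year bias runs from 0.05 to 2.0 points, with 0.25 to 0.5 at middle values. With 96 of 100 surviving, the 95% limits span 8.8 points (90.1 to 98.9), so the bias is usually small against sampling error. It is still worth removing, because it is mainly upward and a confidence interval does not allow for it. These sizes rest on the assumed rates and, for reoperation-then-revision sequences, on reoperation counting as failure.

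**What to change.** Replace the date item with wording such as: *Please list every operation on this knee since [DOS], with the type, date and reason for each.* Take the earliest operation that meets the study's failure definition as the failure date. Because the type is recorded, this works whether or not reoperation counts.

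At the five- and ten-year calls:
- keep the look-back to the index surgery, so that patients missed earlier are covered;
- read back any operations already on file before asking about others;
- keep a recorded failure at its first date unless a record corrects it.

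The cost is a change of script wording, spreadsheet rows that allow more than one operation per knee, and about a minute more on the call for patients who answer yes. No extra patients or staff are needed.
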